Treatment Plan	This randomized, controlled, phase II clinical study is designed to assess the efficacy of preemptive treatment with topical steroids in preventing the papulopustular eruption induced by epidermal growth factor receptor inhibitor (EGFRI) treatment in cancer patients. Participants will be followed up for 6 weeks of twice daily application of triamcinolone cream to the face, chest, and back.		
Statistical Methodology	For all analyses, a type I error of 5% (two-sided) will be used to test for statistical significance and will be performed using SAS v9.2 (SAS Institute, Cary, NC). Randomization will be stratified according to skintype.		

Version Date: 01-25-2021 5

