2.0 OBJECTIVES & ENDPOINTS

2.1 Primary Objective & Endpoint

To assess the difference in percentage of participants who develop a grade 2 or greater rash in the control group as compared to the case group of preemptive treatment with topical steroids (triamcinolone 0.1% cream for application to face, chest and back) when administered concomitantly for 6 weeks with erlotinib, cetuximab, panitumumab, afatinib or osimertinib to prevent papulopustular eruptions.

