9.0 STATISTICAL CONSIDERATIONS

9.1 Study Design/Study Endpoints

This study is a randomized control trial with a control arm and a treatment arm. The primary study endpoint is defined as the percentage of patients developing a grade 2 rash or greater.

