9.2 Sample Size and Accrual

A total of 80 patients will be enrolled in the study. Assuming a low 3% lost to follow-up rate, we will aim for a sample size of 84 patients (42 patients per treatment group), which will provide 80% power to detect a difference in rash incidence of 30% between the steroid arm and control group (i.e. 45% in the steroid arm versus 75% in the control group).

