9.3 Data Analyses Plans

The primary objective will be to assess and compare the incidence of rash in patients treated preemptively with topical steroids and control patients.

Proportions experiencing EGFRI-induced papulopustular eruption (any severity) by 6 weeks will be estimated and compared using the Mantel-Haenszel Chi-Square test to account for the stratification factor in the randomization procedure. A test for homogeneity will be performed to assess the adequacy of a common odds ratio (OR). Results will be summarized using an OR and 95% confidence interval. Supportive analysis will use a generalized estimating equations (GEE) approach, which will allow modeling of the proportion of patients with rash over time. Fixed factors for treatment group, time and the treatment group by time interaction will evaluate time differences in the proportion of patients with rash between the two treatment arms while accommodating repeated measures over time.

The secondary objective, maximum grade severity during the 6-week study period will be tabulated by treatment group and compared using the Cochrane Armitage test for trend.

Secondary endpoints will also include comparisons across the study arms to assess changes in quality-of-life scores from baseline, as measured by the FACT-EGFRI-18 questionnaire. FACT-EGFRI-18 scores will be presented as the median percentage from baseline. Scores at 6 weeks will be compared using the nonparametric Van Elteren test, which combines stratum-specific Wilcoxon Rank-Sum statistics with weights inversely proportional to stratum sizes. Differences in adherence to chemotherapy treatment over the 6 weeks will be compared across the two study arms using the Mantel-Haenszel Chi-Square test. The incidence of adverse events will also be compared across treatment arms with a Fisher exact test.

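### Objective 2.1 and the sample size are on the risk-difference scale, but the only effect estimate with an interval that Section 9.3 pre-specifies is an odds ratio

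*Combined protocol and SAP*

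**What the plan says.** Section 2.1 states the primary objective as a contrast of percentages: "To assess the difference in percentage of participants who develop a grade 2 or greater rash", control arm against preemptive arm. Section 9.1 agrees: "The primary study endpoint is defined as the percentage of patients developing a grade 2 rash or greater". Section 6.2 also defines the endpoint as a percentage.

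Section 9.2 sizes the trial on the same scale. The planned 84 patients, 42 per arm, are to give "80% power to detect a difference in rash incidence of 30% between the steroid arm and control group", with the rates spelled out as "i.e. 45% in the steroid arm versus 75% in the control group".

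Section 9.3 plans to estimate the proportions with rash by 6 weeks and to compare them by a Mantel-Haenszel chi-square test that accounts for the skin-type stratification. It adds a homogeneity test for a common odds ratio and then says: "Results will be summarized using an OR and 95% confidence interval". The supportive GEE model describes the proportion with rash over time but names no link function, contrast or interval. No section specifies a risk difference with a confidence interval.

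**The concern.** The trial asks its question and justifies its size in percentage points, yet the pre-specified effect estimate is on another scale. Two things follow.

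First, no planned interval can be set directly against the 30 points in Section 9.2. An interval for the odds ratio does not convert to one for the difference without the control rate, and that rate will itself be estimated from about 40 patients.

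Second, the event is common, so the odds ratio lies well away from the risk ratio. The earlier trials described in Section 1.2 are reported as percentages (29% versus 62%, and 17% versus 55%, for grade 2 or greater toxicity or rash). A reader comparing this trial with those could take an odds ratio of 0.27 for a 73% reduction in risk, when the planned relative reduction is 40%.

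**Working it through.** **Inputs.** Rates of 45% (steroid) and 75% (control), 80% power, 42 per arm and 3% loss to follow-up come from Section 9.2. Two-sided 5% type I error comes from the Study Summary.

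**The plan's own figure.** With pooled variance and no continuity correction, and mean rate 0.60:

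n per arm = [1.960 × √(2 × 0.60 × 0.40) + 0.842 × √(0.45 × 0.55 + 0.75 × 0.25)]² / 0.30² = 40.7, so 41 per arm.

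Power is 81.3% at 42 per arm and 79.3% at 40 per arm. The stated sample size reproduces.

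**The planned effect on three scales.**
- Odds ratio: (0.45/0.55) / (0.75/0.25) = 0.273
- Risk ratio: 0.45/0.75 = 0.60
- Risk difference: 0.45 - 0.75 = -0.30

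Read as a risk ratio, 0.27 suggests a 73% reduction (1 - 0.27). The actual relative reduction is 40% (1 - 0.60).

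**Precision if the planned rates are observed.** These intervals are unstratified, because the documents give no stratum sizes or stratum-specific rates.

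- SE of the difference = √[(0.45 × 0.55 + 0.75 × 0.25)/n], and the interval is -0.30 ± 1.96 × SE.
- SE of the log odds ratio = √[1/(0.45n) + 1/(0.55n) + 1/(0.75n) + 1/(0.25n)], and the interval is exp(ln 0.273 ± 1.96 × SE).

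| n per arm | SE of difference | 95% CI for difference (points) | 95% CI for odds ratio |
|---|---|---|---|
| 40 | 0.104 | -50.4 to -9.6 | 0.11 to 0.70 |
| 41 | 0.103 | -50.2 to -9.8 | 0.11 to 0.70 |
| 42 | 0.102 | -49.9 to -10.1 | 0.11 to 0.69 |

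**What an odds ratio of 0.273 implies for the difference.** For control rate c, the treated odds are 0.273 × c/(1 - c), the treated rate is odds/(1 + odds), and the difference is treated rate minus c.

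| Control rate | Treated rate | Difference (points) |
|---|---|---|
| 30% | 10.5% | -19.5 |
| 45% | 18.2% | -26.8 |
| 55% | 25.0% | -30.0 |
| 62% | 30.8% | -31.2 |
| 66% | 34.6% | -31.4 |
| 75% | 45.0% | -30.0 |
| 90% | 71.1% | -18.9 |

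The largest difference, about -31.4 points, falls at a control rate near 66%. The range is therefore about -19 to -31 points over control rates of 30% to 90%, and about -30 to -31 over 55% to 75%.

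**The case against.** The strongest reply is that this is a choice of effect measure and not an error. An odds ratio with a 95% CI is a standard companion to a Mantel-Haenszel test, and planning on 45% versus 75% is equally planning on an odds ratio of 0.27. The test is valid for the null of no difference, and no error rate or sample size changes. All of that stands, and it limits the point to a gap in planned estimation.

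A reader might infer that the trial will never report a difference, or will report only an odds ratio. The documents do not support that. Section 9.3 says the proportions will be estimated, so a crude difference, and a simple interval for it, can be derived from the arm percentages and arm sizes. Showing both percentages also reduces the risk that the odds ratio is misread. What is absent is a pre-specified stratified estimate with its interval.

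A reader might also infer that the odds ratio leaves the difference wide open. Algebraically it does not fix the difference, but the spread comes mainly from control rates far from those the documents lead one to expect. Section 1.2 gives 55% and 62% in the comparator arms of two earlier trials, and Section 9.2 assumes 75%. At those three rates, 0.273 gives -30.0, -31.2 and -30.0 points.

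Finally, if baseline rates differ by skin type, a common odds ratio implies unequal differences in the two strata. The stratified risk difference is then a weighted average, and its weights should be stated. This argues for stating the method, not for omitting the estimate.

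**Conclusion.** The point holds as a gap in pre-specified estimation. The stated objective is a difference in percentages, and the plan contains no stratified estimate of that difference and no interval for it. At the planning rates, the missing result would be -30 points with a 95% CI of about -50 to -10. The planned result for the same data would be an odds ratio of 0.27 with an interval of about 0.11 to 0.70. These figures assume the planned rates are observed, 41 or 42 evaluable patients per arm, and no allowance for stratification.

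Nothing here faults the test or the 84 patients, and nothing requires the odds ratio to be dropped or demoted.

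A separate mismatch bears on the remedy. Section 9.3 analyses rash of any severity, while Sections 2.1, 6.2 and 9.1 specify grade 2 or greater. A risk difference added to the any-severity analysis would still miss the stated objective.

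**What to change.** Add a sentence to Section 9.3: the difference between arms in the proportion with grade 2 or greater rash by 6 weeks will be estimated as the Mantel-Haenszel risk difference stratified by skin type (Fitzpatrick I-III, IV-VI), with a 95% CI, and reported alongside the common odds ratio. State the weights; the usual ones are (treated n × control n)/(stratum total). A stratified risk ratio can be shown as well. Keep the Mantel-Haenszel chi-square as the test.

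In the same edit, reconcile the any-severity wording in Section 9.3 with the grade 2 or greater endpoint in Sections 2.1, 6.2 and 9.1.

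The risk difference needs no extra patients, visits or data. It adds an estimate and not a test, so type I error is unchanged. It is a closed-form weighted average over two strata, so the programming cost is small. The endpoint wording is a further edit and needs a decision by the investigator.

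### The maximum-severity trend test and the supportive GEE leave out the skin-type stratum used in randomisation; if skin type predicts rash, a little power is lost

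*Combined protocol and SAP*

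**What the plan says.** The Study Summary (Statistical Methodology) states: "Randomization will be stratified according to skintype". Section 4.2.1 defines two strata, Fitzpatrick I–III and IV–VI.

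Section 9.3 then treats its analyses differently:

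| Analysis in section 9.3 | Method | Stratum used? |
|---|---|---|
| Rash incidence by 6 weeks | Mantel-Haenszel, chosen to reflect the stratified randomisation | Yes |
| Quality of life at 6 weeks | Van Elteren | Yes |
| Adherence to chemotherapy | Mantel-Haenszel | Implied by the method |
| Supportive rash model | GEE: "Fixed factors for treatment group, time and the treatment group by time interaction" | Not listed |
| Maximum severity | "maximum grade severity during the 6-week study period will be tabulated by treatment group and compared using the Cochrane Armitage test for trend" | Not listed |

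No general statement says that every comparison adjusts for skin type. The documents do not give the share of patients in each stratum, the effect of skin type on rash, any blocking scheme, or the expected distribution of grades.

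**The concern.** Maximum severity is the first secondary objective listed in section 2.2. An analysis that ignores a prognostic stratification factor counts the difference between strata as noise. If the randomisation has already balanced the arms within strata, that noise cannot reach the treatment comparison. The variance used is then too large and the test is conservative. If balance is not forced, the noise does reach the comparison and costs power. Either way, what is at stake is sensitivity on a secondary test and a supportive model in a trial of about 80 patients.

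The GEE raises one further issue. The Mantel-Haenszel analysis reports a common within-stratum odds ratio. A GEE without the stratum estimates an odds ratio averaged over skin types. Odds ratios are non-collapsible, so the two can differ even with perfect balance if skin type matters.

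**Working it through.** **1. The plan's own figure.** Inputs: "a type I error of 5% (two-sided) will be used to test for statistical significance" (Study Summary); and from section 9.2, "which will provide 80% power to detect a difference in rash incidence of 30% between the steroid arm and control group", with "45% in the steroid arm versus 75% in the control group". The pooled formula per arm is

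n = [z₀.₉₇₅ √(2p̄q̄) + z₀.₈₀ √(p₁q₁ + p₂q₂)]² / (p₁ − p₂)²

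With p̄ = 0.60: 1.960 × √0.48 = 1.358; 0.842 × √(0.2475 + 0.1875) = 0.555; (1.358 + 0.555)² / 0.09 = 40.7, so 41 per arm. Power is 79.3% at 40, 80.3% at 41 and 81.3% at 42 per arm. Section 9.2 says "A total of 80 patients will be enrolled in the study" and "we will aim for a sample size of 84 patients (42 patients per treatment group". Reading 80 as the evaluable number, 80 / 0.97 = 82.5, which becomes 83, or 84 for equal arms. The stated size is reproduced, and nothing below changes it.

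**2. Why omitting the stratum matters.** Let y be the maximum grade, T the sum of y in the treated arm minus n₁ȳ, and z = T/√V.
- Unstratified: V = (n₁n₀/N) s². Here s² includes the between-stratum part π(1 − π)Δ², where π is the share in one stratum and Δ the difference in mean grade between strata.
- Stratified: T and V are summed over the two strata, so only within-stratum variance enters.

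If arms are balanced within strata, T varies only through the within-stratum part, so Var(T)/V ≈ 1 − R², where R² is the share of grade variance due to skin type. In simulation at odds ratio (OR) 5 with equal strata, the unstratified z has SD 0.924 under the null. Hence R² ≈ 1 − 0.924² = 0.146, and the standard error is 1/0.924 = 1.08 times too large. The implied level is 2[1 − Φ(1.96/0.924)] = 2[1 − Φ(2.12)] = 3.4%, which is also the simulated level. At Δ = 0 there is no effect.

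**3. Trend test, blocks of four within strata (assumed).** The simulation used 80 patients, 1:1, with 20,000 runs per cell. Other assumptions: 10%, 20%, 30% or 50% in the smaller stratum; control-arm grades ≥1/≥2/≥3 of 75%/45%/12%; treatment log-OR −1.16. Ranges run over the stratum shares.

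| Skin-type OR | Level, unstratified | Level, stratified | Power, unstratified | Power, stratified | Change in power (points) |
|---|---|---|---|---|---|
| 1 | 5.0–5.4% | 4.8–5.3% | 79.1–79.5% | 78.7–79.1% | −0.6 to −0.3 |
| 2 | 4.5–5.1% | 4.7–5.0% | 78.1–79.0% | 78.6–78.9% | −0.3 to +0.5 |
| 3 | 4.3–4.8% | 4.9–5.1% | 75.9–78.5% | 77.7–78.9% | +0.2 to +2.2 |
| 5 | 3.4–4.3% | 4.8–5.0% | 71.2–76.6% | 76.8–77.8% | +1.2 to +5.7 |

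A separate blocked simulation at 80 patients gave unstratified levels of about 4.6% (OR 2), 3.9–4.2% (OR 3) and 3.5–3.7% (OR 4.5), with power losses of about 1, 2–3 and 4–5 points. Another, with 82 patients balanced within strata, different grade cut-points and skin-type log-odds −1.5 (OR 4.5), gave 3.3–3.7% against 4.8–4.9% stratified, and power 72–75% against 76–79%. With no skin-type effect, its powers were 83.7% and 83.6%.

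**4. Trend test without forced balance.** With simple randomisation, OR 3 and 30% in the smaller stratum, the unstratified level is 5.1%. Power is 75.4%, against 77.1% stratified. The level holds and only power is lost.

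**5. GEE.** The simulation used 80 patients, three visits, independence working correlation, robust standard errors and the visit-averaged treatment effect, with 3,000 runs per cell and blocks of four. Assumptions: 20%, 30% or 50% in the smaller stratum; patient random-intercept SD 1.5; conditional treatment log-OR −1.5; skin-type log-OR multiplied by 1.3 on the patient-specific scale.

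| Skin-type OR | Level, no stratum | Level, with stratum | Change in power (points) |
|---|---|---|---|
| 1 | 5.1–5.5% | 5.2–5.6% | +0.1 to +0.3 |
| 2 | 4.9–5.2% | 5.6–5.7% | +0.8 to +1.2 |
| 3 | 3.8–4.9% | 4.8–5.9% | +1.4 to +3.2 |
| 5 | 2.6–3.6% | 5.0–5.5% | +3.0 to +6.1 |

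A longer run (8,000 per cell, smaller stratum 10–50%) gave 5.5–5.8% adjusted against 5.0–5.4% unadjusted at OR 2, and 5.1–5.6% against 4.3–5.0% at OR 3, with simulation error of about 0.25 points. Part of the GEE's apparent power gain is therefore a higher rejection rate under the null.

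**The case against.** The strongest reply is that every consequence is conditional. The documents report no effect of skin type on rash; section 1.1 ties rash frequency to the particular EGFR inhibitor and its dose. An odds ratio of 4.5 to 5 between two broad skin-type groups is a large assumption, and at 2 the change is effectively nil. That stands, and is why the size is given as a range starting at zero.

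A reader might infer that the stated 5% level is not delivered, or that the error bars do not match the design. The documents do not support this as a flat statement. It needs both a skin-type effect and forced balance within strata, and neither is stated. The departure would in any case be conservative, so false positives are not inflated. The plan also reports no interval for the trend test, so error bars could refer only to the GEE.

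The GEE can also be defended as serving another purpose, since section 9.3 uses it to look at rash over time, and the listed factors are not said to be exhaustive. This has some force: a supportive model need not repeat the main contrast. But if the stratum is meant to be included, the plan should say so.

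Finally, a reader might think adding the stratum is free everywhere. That is nearly true for the trend test, where it cost 0.3 to 0.6 points of power at OR 1. It is not true for the GEE.

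**Conclusion.** The omission is real but minor. Section 9.3 applies its stratification principle to the rash-incidence and quality-of-life tests and, as written, not to the maximum-severity test or the GEE.

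Under an assumed skin-type odds ratio of 1 to 5, the unstratified trend test loses nothing at 1, about 0 to 1 point of power at 2, 0 to 3 points at 3, and about 1 to 6 points at 4.5 to 5. If balance is also forced within strata, its level is about 4.5–5% at 2, 4–5% at 3 and roughly 3.5–4.3% at 4.5 to 5 (lowest single result 3.3%). These figures rest on assumed stratum shares, grade distribution and treatment effect.

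It would be wrong to read this as a threat to the main result or to the sample size. The rash-incidence test is stratified, and 84 patients stands.

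**What to change.** In section 9.3, before any comparative data are examined:

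1. Replace the Cochran-Armitage test with its stratified form: a Mantel trend test (CMH row-mean-score statistic) on maximum grade, controlling for Fitzpatrick stratum I–III versus IV–VI. The stratum is already needed for randomisation, so this requires one line of text and no new data or patients. The cost in power is essentially nil.
2. Add the skin-type stratum as a fixed factor in the GEE, so that it matches the stratified Mantel-Haenszel odds ratio. State that the resulting odds ratio is conditional on stratum, and specify a small-sample correction to the robust standard error.
3. State whether randomisation is blocked within strata, so that a reader can tell whether the unstratified level would have been affected.

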Obtain demographic data, medical history, medication list, history of drug reactions, personal and family hx of acne/rosacea; perform complete skin exam; obtain standard digital photos of face, chest, and back; count baseline number of macules/papules/pustules on face, chest, and back; obtain optional nasal swab culture

Administer FACT-EGFRI-18 questionnaire

Randomly assigned 1:1

Initiate cetuximab, erlotinib, panitumumab, afatinib or osimertinib therapy Initiate topical triamcinolone 0.1% cream

Initiate cetuximab, erlotinib, panitumumab, afatinib or osimertinib therapy

At any time point, if grade 2 or greater rash develops, initiate treatment as deemed necessary, such as topical steroids or oral antibiotics. Participants will still be followed for the six week duration of study.

incidence and severity

Skin exam. di

Adverse side effects assessment, FACT-EGFRI-18, review of patient diary incidence and severity
Adverse side effects assessment, FACTEGFRI-18, review of patient diary

nt of rash

Week 4

Skin exam, digital photos, assessment of rash

Week 6

Skin exam, digital photos, assessment of rash incidence and severity
Adverse side effects assessment, FACT-EGFRI-18, review of patient diary; obtain optional nasal swab

Week 4

Skin exam, digital photos, assessment of rash

Week 6

Skin exam, digital photos, assessment of rash incidence and severity

Adverse side effects assessment, FACT-EGFRI-18, review of patient diary; obtain optional nasal swab

STUDY SUMMARY

Title	A Randomized Phase II Study of Topical Steroids as Preemptive Therapy for Epidermal Growth Factor Receptor Inhibitor-Induced Papulopustular Eruption		
Short Title	A Study of Topical Steroids as Preemptive Therapy EGFR Inhibitor- Induced Papulopustular Eruption		
Version	07-02-2019		
Study Design	Randomized Control Trial		
Study Center(s)	Robert H. Lurie Cancer Center		
Objectives	To determine the efficacy of preemptive treatment with topical steroids (triamcinolone 0.1% cream for application to face, chest and back) when administered concomitantly for 6 weeks with erlotinib, cetuximab, panitumumab, afatinib or osimertinib to prevent papulopustular eruptions.		
Sample Size	84		
Diagnosis & Key Eligibility Criteria	Patients must have a histologically or cytologically confirmed cancer diagnosis for which EGFRI treatment is indicated, and must be starting treatment with cetuximab, erlotinib, panitumumab, afatinib or osimertinib.		

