2.2 Secondary Objectives & Endpoints

- 2.2.1 To assess the difference in maximum severity of rash between the preemptive treatment group and the reactive treatment group.
- 2.2.2 To assess the difference in change in quality-of-life due to rash between the two treatment groups.
- 2.2.3 To determine whether there is a difference in adherence to chemotherapy between the two treatment groups.
- 2.2.4 To determine if the results of baseline nasal swab cultures are associated with rash development or rash severity.

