3.2 Exclusion Criteria

- 3.2.1 Patients who have used systemic or topical steroids within 7 days of trial registration, or start systemic or topical steroids for reasons unrelated to trial during the 6-week follow up period. Systemic steroids as part of chemotherapy regimen are allowed.
- 3.2.2 Patients who have used antibiotics within 7 days of trial registration, or start antibiotics for other conditions during the 6-week follow up period
- 3.2.3 History of allergic reactions to topical steroids
- 3.2.4 Patients with any rash at the time of study registration
- 3.2.5 Uncontrolled intercurrent illness including, but not limited to, ongoing or active infection, symptomatic congestive heart failure, unstable angina pectoris, cardiac arrhythmia, or psychiatric illness/social situations that would limit compliance with study requirements.

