4.2 Treatment Administration

4.2.1 Treatment arm: Triamcinolone 0.1% Cream

Eligible patients will be randomly assigned to either the treatment group to receive topical triamcinolone 0.1% cream for application to the face, chest and back, or will be assigned to the control group to receive no preemptive treatment. Patients will be assigned to either group in a randomized manner, stratified according to Fitzpatrick skin type. Stratification group 1 will consist of patients with Fitzpatrick skin type I-III. Stratification group 2 will consist of patients with Fitzpatrick skin type IV-VI. The Fitzpatrick skin typing test is a numerical classification schema for human skin color, as explained below (Fitzpatrick TB. The validity and practicality of sun reactive skin types i through iv. 1988. Archives of Dermatology. 124(6):869-871.)

• Type I (scores 0–6) always burns, never tans (pale white; blond or red hair; blue eyes; freckles)

NU Study Number: *JNC06142016* Other Study Numbers: STU00203631; NU 16D05

- **Type II** (scores 7–13) usually burns, tans minimally (white; fair; blond or red hair; blue, green, or hazel eves)
- **Type III** (scores 14–20) sometimes mild burn, tans uniformly (cream white; fair with any hair or eye color)

- Type IV (scores 21–27) burns minimally, always tans well (moderate brown)
- Type V (scores 28–34) very rarely burns, tans very easily (dark brown)
- Type VI (scores 35–36) Never burns, never tans (deeply pigmented dark brown to darkest brown)

If the patient is randomized to the treatment group, then the study team has the option to distribute the study drug either in person during a clinic visit or by shipping the study drug to the patient after success registration. If shipping the study drug to the patient, then we will use a courier such as FEDEX that provides tracking information and overnight shipments are preferred. The packaging will be secure and tamper proof, and the patient's name and address information will be verified.

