5.0 STUDY PROCEDURES

	Screening	On Treatment		
Time Period	Baseline	Week 2	Week 4	Week 6
Assessment or Activity				
Informed Consent	×			
Obtain history ¹	×			
Complete skin exam ²	Х	Х	Х	Х
Standardized digital photos of face, chest, and back	Х	X	Х	Х
FACT-EGFRI-18 Questionnaire	Х	Х	Х	Х
Assess for adverse side effects		X	X	Х
Review of patient diary		X	X	Х
Application of topical triamcinolone 0.1% cream	Х	X	X	_
Nasal Swab ³	×			Х

NU Study Number: JNC06142016 Other Study Numbers: STU00203631; NU 16D05

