6.3 Secondary Endpoints

- **6.3.1** The difference in maximum severity of rash between the preemptive treatment group and the reactive treatment group
- **6.3.2** The difference in change in quality of life due to rash between the two treatment groups.
- **6.3.3** The difference in adherence to chemotherapy between the two treatment groups.
- **6.3.4** The association of baseline nasal swab cultures and development of rash or rash severity.

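### Section 9.3 leaves open which week-6 FACT-EGFRI-18 variable is tested, and on no reading is the pre-randomisation baseline used as a covariate

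*Combined protocol and SAP*

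**What the plan says.** Objective 2.2.2 reads "To assess the difference in change in quality-of-life due to rash between the two treatment groups", and endpoint 6.3.2 repeats it: "The difference in change in quality of life due to rash between the two treatment groups".

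The quality-of-life paragraph of section 9.3 describes the outcome in three ways in consecutive sentences. It opens by announcing "comparisons across the study arms to assess changes in quality-of-life scores from baseline". It then continues: "FACT-EGFRI-18 scores will be presented as the median percentage from baseline. Scores at 6 weeks will be compared using the nonparametric Van Elteren test". The test is described as combining rank-sum statistics within strata. The only stratification factor in the protocol is skin type (section 4.2.1: "Patients will be assigned to either group in a randomized manner, stratified according to Fitzpatrick skin type"), in two groups, I-III and IV-VI. No baseline term is named.

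The baseline exists. The study schema lists "Administer FACT-EGFRI-18 questionnaire" ahead of random assignment, and the section 5.0 table schedules the questionnaire at baseline and weeks 2, 4 and 6. Appendix 1 prints 18 items, each scored 0 to 4. Section 3.2.4 excludes "Patients with any rash at the time of study registration".

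**The concern.** The sentence that names the test mentions only the score at week 6, while the objective, the endpoint and the opening of the same paragraph concern change. A statistician working from section 9.3 could apply the Van Elteren test to the week-6 score, the absolute change or the percentage change. These are different tests that rank patients differently, and nothing in the plan stops the choice from being made after the data are seen.

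None of the three uses the baseline as a covariate. An unadjusted change score subtracts the baseline with a fixed coefficient of one, which can add noise when the correlation is low. A baseline measured before randomisation is a legitimate covariate that costs nothing to use, so leaving it out gives up precision in a trial of about 80 patients.

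**Working it through.** **Inputs.** From the documents: 1:1 allocation; two-sided 5% for all analyses (study summary); 80 patients, raised to 84 for 3% loss (section 9.2), so 40 per arm is used here. The 80% power in 9.2 applies only to the primary endpoint, 45% versus 75% with rash. It reproduces (81.3% at 42 per arm, 79.3% at 40, pooled-variance normal approximation). The documents give no effect size, SD, correlation or power for quality of life, so there is no plan figure to reproduce for this endpoint. Assumed: baseline to week-6 correlation r of 0.2, 0.4 and 0.6; ratio k of baseline SD to week-6 SD of 0.5 and 1.

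**Formula.** In week-6 SD units, detectable difference = (1.96 + 0.84) × √(2/40 × factor) = 0.626 × √factor, where the factor is:

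- week-6 score: 1
- baseline-adjusted: 1 − r²
- unadjusted change: 1 + k² − 2rk

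| | r = 0.2 | r = 0.4 | r = 0.6 |
|---|---|---|---|
| Week-6 score: factor 1 | 0.626 | 0.626 | 0.626 |
| Adjusted: factor 0.96, 0.84, 0.64 | 0.614 | 0.574 | 0.501 |
| Change, k = 0.5: factor 1.05, 0.85, 0.65 | 0.642 | 0.578 | 0.505 |
| Change, k = 1: factor 1.6, 1.2, 0.8 | 0.792 | 0.686 | 0.560 |

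**Comparisons.** Change is less precise than the week-6 score when 1 + k² − 2rk > 1, that is when r < k/2. The change factor minus the adjusted factor is (1 + k² − 2rk) − (1 − r²) = (k − r)², which is never negative. In this approximation adjustment is therefore at least as precise as either alternative, whatever r and k are.

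**Rank-test check.** A simulation used 40 per arm, assumed strata of 60 and 20 patients, normal scores and a true effect of 0.626 SD. Power at r = 0.2, 0.4, 0.6:

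| | k = 0.5 | k = 1 |
|---|---|---|
| Van Elteren, week-6 score | 76-77% | 76-77% |
| Van Elteren, change | 74, 83, 91% | 56, 69, 85% |
| Stratified rank ANCOVA, week-6 score | 77, 82, 90% | 76, 81, 90% |

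Rank ANCOVA stays within about a point of the best option in every cell. Unadjusted change falls about 20 points short in the worst cell (56% against 76%).

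**Does adjustment remove the score-versus-change question?** For linear ANCOVA it does. If Y − B = a + τ·arm + βB + error, then Y = a + τ·arm + (β + 1)B + error, so τ and its standard error are identical. For rank ANCOVA it does not, because ranking the score and ranking the change are different operations. In simulation the two versions disagreed on significance in about 4-10% of trials. The ranked outcome must be named.

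**Percentage summary.** Summed as printed, the total runs from 0 to 18 × 4 = 72. A percentage from baseline is undefined at 0 and unstable just above it: a 4-point rise is 400% from a baseline of 1 and 20% from a baseline of 20. Low baselines are plausible because rash at registration is an exclusion.

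**The case against.** The strongest reply is that the three sentences should be read together: the first gives the quantity (change), the second the presentation scale, the third the time point and test. On that reading the test matches the endpoint and the baseline is used. This is a natural reading, and a claim that section 9.3 contradicts the endpoint, or discards the baseline altogether, would go too far. But it still leaves absolute against percentage change open. It also leaves an unadjusted change score, the option that loses most when the correlation is low.

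A second reply is that Van Elteren is a valid stratified test and baseline adjustment is only a preference. The validity stands. The preference label does not: the covariate is already collected, and adjustment matches or improves precision under the normal approximation.

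A third reply is that the size rests on assumption. That stands. At r = 0.2 the gain over the week-6 score is 0.63 against 0.61 SD, which is nothing of consequence.

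The percentage point also has limits. Appendix 1 does not give the scoring direction, and if scoring is reversed the problem largely disappears. A zero total needs the lowest answer on all 18 items, which include dry eyes, nail sensitivity and hair loss as well as rash-type symptoms.

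**Conclusion.** The point holds as a minor one. Section 9.3 does not fix which of three variables is tested, and under each of them the pre-randomisation baseline is not a covariate. The need to name one variable depends on no assumption. The precision gain does. Over assumed correlations of 0.2 to 0.6, adjustment lowers the detectable difference from 0.63 SD for the week-6 score to between 0.61 and 0.50 SD. Against unadjusted change, the gain ranges from almost nothing when the baseline SD is half the week-6 SD (0.64 to 0.51 SD unadjusted) to 0.79 against 0.61 SD when the SDs are equal and the correlation is 0.2.

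Three stronger conclusions are tempting and unsupported:

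- **Bias.** A reader might infer that the comparison is biased. With complete week-6 data, randomisation makes it valid on any reading. Section 4.7 does allow withdrawal, but missing data are a separate matter.
- **Any adjustment settles score versus change.** Only linear ANCOVA does.
- **A count of patients with an undefined percentage.** The documents give neither the scoring direction nor the share of zero baselines, so no count can be stated.

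The endpoint is secondary and unpowered, and the primary endpoint and sample size are unaffected.

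**What to change.** In section 9.3, name one analysis of the week-6 FACT-EGFRI-18 score:

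- ANCOVA of the week-6 score on arm, baseline score and skin-type stratum (I-III, IV-VI), reporting the adjusted arm difference with a 95% confidence interval; or
- to stay nonparametric, rank ANCOVA stratified by skin type, with the week-6 score named as the ranked outcome and the baseline score as covariate.

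Replace the percentage summary with absolute change from baseline, and state how the 18 items are scored and in which direction.

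The cost is a few sentences in 9.3 and no new data. If the correlation proves low, the precision gain is close to nil, but the tested variable is still fixed in advance.
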